6.6.3 Sensitivity Analysis

The following sensitivity analysis will be performed on the primary efficacy endpoint (the clinical response rate at Day 57) and the first secondary efficacy endpoint (the clinical remission rate at Day 57).

For these analyses, the following rules will apply.

[REDACTED]

[REDACTED]

[REDACTED]

[REDACTED]

In addition, the primary efficacy analysis will also be performed for the per-protocol population.

6.6.4 Subgroup Analysis

There is no pre-specified subgroup analysis for this study.

6.6.5 Exploratory Analysis

- **Endoscopic response rate by Day 57, as defined by a ≥ 2 -points reduction from baseline in UCEIS score via central reading.**

The UCEIS score will be calculated as the sum of the scores of all descriptors. The higher the score, the worse the UC. Baseline total UCEIS score minus Day 57 UCEIS score will be used to calculate the number of subjects who have a ≥ 2 points reduction. With a difference ≥ 2 points will be considered as endoscopic response. Missing value will be imputed based on the description from Section 5.2.

Statistical Analysis Plan

Sponsor Name: Bridge Biotherapeutics, Inc.
Sponsor Protocol ID: BBT401-UC-005

The actual and change from baseline will be presented. The number and proportion of subjects with the 95% CI of endoscopic response rate at Day 57 will be calculated using the exact binomial method for each treatment. The Fisher's exact test will be used to evaluate any differences between treatments at Day 57 and will be summarised for the induction phase by treatment group for ITT Population.

- **Endoscopic response rate at Day 57, as defined by a reduction of ≥ 1 grade in the Mayo endoscopic subscore**

The Mayo endoscopic subscore will be based on Part 4 of the total Mayo score - "Investigator-reported Findings on endoscopy". The change in endoscopic score is calculated as the difference between the baseline and Day 57 scores. A difference of ≥ 1 grade is considered as endoscopic response. Missing values will be imputed based on the description from Section 5.2.

The number and proportion of subjects with the 95% CI of endoscopic response rate at Day 57 will be calculated using the exact binomial method for each treatment. The Fisher's exact test will be used to evaluate any differences between treatments at Day 57 and will be summarised for the induction phase by treatment group for ITT Population.

- **Modified Mayo remission rate at Day 57, as defined by a $\text{mMCS} \leq 2$, $\text{RBS}=0$, $\text{mESS} \leq 1$, $\text{SFS}=0$ or (1 if at least 1 point drop from baseline)**

The modified Mayo remission will be based on the Total Mayo Score with all the following 4 conditions are satisfied: 1. $\text{mMCS} \leq 2$, and 2. Rectal Bleeding Score=0, and 3. $\text{mESS} \leq 1$, and 4. Stool Frequency Score=0 or (1 if at least 1 point drop from baseline), where mMCS will be collected in the Modified Mayo Score form as the sum of RBS , mESS and SFS . Missing values will be imputed based on the description from Section 5.2.

The number and proportion of subjects with the 95% CI of modified Mayo remission rate at Day 57 will be calculated using the exact binomial method for each treatment. The Fisher's exact test will be used to evaluate any differences between treatments at Day 57 and will be summarised for the induction phase by treatment group for ITT Population.

- **Symptomatic remission rate at Day 57, as defined by $\text{RBS}=0$, $\text{SFS}=0$**

The symptomatic remission rate at Day 57 will be based on the Rectal Bleeding Score =0 and Stool Frequency Score=0 from Total Mayo Score. Missing values will be imputed based on the description from Section 5.2.

Statistical Analysis Plan

Sponsor Name: Bridge Biotherapeutics, Inc.
Sponsor Protocol ID: BBT401-UC-005

The number and proportion of subjects with the 95% CI of symptomatic remission rate at Day 57 will be calculated using the exact binomial method for each treatment. The Fisher's exact test will be used to evaluate any differences between treatments at Day 57 and will be summarised for the induction phase by treatment group for ITT Population.

- **Inflammatory Bowel Disease Questionnaire (IBDQ) total score, as measured by change from baseline**

The IBDQ is a health-related quality-of-life (HRQoL) tool measuring bowel, systemic, emotional, and social function. Scores for each question range between 1 and 7, reflecting poor to good HRQoL, for a range of possible total scores from 32 to 224. In terms of the 4 aspects of patients live and their corresponding questions, it is summarised in the following table.

Aspects	Questions	Range of Score
Bowel	1, 5, 9, 13, 17, 20, 22, 24, 26, 29	10 to 70
Systemic	2, 6, 10, 14, 18	5 to 35
Emotional	3, 7, 11, 15, 19, 21, 23, 25, 27, 30, 31, 32	12 to 84
Social Function	4, 8, 12, 16, 28	5 to 35
Total Score	1~32	32 to 224

Descriptive statistics on total score and its four aspects: bowel, systemic, emotional, and social function at each scheduled visit as well as change from baseline will be calculated for each phase and by treatment group for the ITT Population.

The following categories with number and percentage of subjects will also be presented for total score at each post-baseline visit:

- change \geq 16 points from baseline
- total score \geq 170

Mixed Model Repeated Measures (MMRM), with repeated change from baseline values as the dependent variable and baseline values as the covariate variable, will be used to compare the change from baseline to Day 29 and 57 in the IBDQ score between treatment and placebo group. The sample SAS code is provided in Appendix 2. The 95% CI for the difference in the change from baseline will be calculated for each treatment, and the p-value will be provided.

Statistical Analysis Plan

Sponsor Name: Bridge Biotherapeutics, Inc.
Sponsor Protocol ID: BBT401-UC-005

The normality assumption will be checked through the Shapiro-Wilk test. If the normality assumption is violated at the 0.01 level of significance, an additional nonparametric analysis [REDACTED] will be used to compare each treated group to the placebo group.

- **Histologic remission using histologic category**

Subjects will be dichotomized as "histological remission" versus "histological non-remission" based on the option recorded on the CRF. Subjects with histologic category recorded as "histologic near remission" and "Other" will be categorised as "histologic non-remission". On the other hand, those recorded with "histologic healing", "histologic remission", "histologic remission without basal plasmacytosis", and "histologic remission without basal plasmacytosis or increased mucosal eosinophils" will be grouped to "histologic remission".

A shift table (i.e., cross-tabulations "histologic remission" and "histologic non-remission" at screening versus Day 57) in a form of 2 x 2 table will be presented for each treatment.

The number and proportion of subjects within each combined category will be summarised by treatment group for the ITT Population.

- **Biomarkers, including C-reactive protein and faecal calprotectin, as measured by change from baseline**

Descriptive statistics on biomarkers at each scheduled visit as well as change from baseline will be calculated for each phase by treatment group for the ITT Population.

- **Clinical remission at Day 112, as measured by a total Mayo score of ≤ 2 points, with no individual subscore exceeding 1 point.**

Total Mayo Score will be evaluated. Subjects who have a total Mayo score ≤ 2 points, with no individual subscore exceeding 1 point at Day 112, will be considered as achieving clinical remission.

The number and proportion of subjects with the 95% CI of clinical remission rate at Day 112 will be calculated using the exact binomial method for each treatment. The Fisher's exact test will be used to evaluate any differences between treatments at Day 112 for the extension phase by treatment group for the ITT Population.

- **Sustained remission at Day 112.**

Total Mayo Score will be evaluated. Subjects who have a total Mayo score ≤ 2 points, with no individual subscore exceeding 1 point at day 57 and day 112 will be considered as achieving sustained remission at day 112.

The number and proportion of subjects with the 95% CI of sustained remission at Day 112 will be calculated using the exact binomial method for each treatment.

Statistical Analysis Plan

Sponsor Name: Bridge Biotherapeutics, Inc.
Sponsor Protocol ID: BBT401-UC-005

The Fisher's exact test will be used to evaluate any differences between treatments at Day 112 for the extension phase by treatment group for the ITT Population.

- **Clinical response rate at Day 112.**

The number and proportion of subjects with the 95% CI of clinical response rate at Day 112 will be calculated using the exact binomial method for each treatment. The Fisher's exact test will be used to evaluate any differences between treatments at Day 112 for the extension phase by treatment group for the ITT Population.

- **Change from baseline to Day 57 in the Partial Mayo score.**

Mixed Model Repeated Measures (MMRM), with repeated change from baseline values as the dependent variable and baseline values as the covariate variable, will be used to compare the change from baseline to Day 29 and 57 in the partial Mayo score between treatment and placebo group. The sample SAS code is provided in Appendix 2. The 95% CI for the difference in the change from baseline will be calculated for each treatment, and the p-value will be provided.

The normality assumption will be checked through Shapiro-Wilk test of the residuals during the use of MMRM. If the normality assumption is violated at the 0.01 level of significance, an additional nonparametric analysis [REDACTED] [REDACTED] will be used to compare each treated group to the placebo group.

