8.4.2. Exploratory Efficacy Analysis

All subjects in the intent-to-treat population will be included in the exploratory efficacy analysis. The estimate and 95% CI of endoscopic response rate and histological improvement at Day 57, and clinical response rate and the percentage of subjects with clinical remission at

Day 112 will be calculated using the exact binomial method for each treatment. Actual values and change from baseline in Mayo scores, UCEIS scores, IBDQ total score, C-reactive protein, and faecal calprotectin over time will be summarised descriptively. No formal hypothesis will be tested on the exploratory efficacy endpoints.

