2.1 Study Objectives

The primary objective of this study is to explore the efficacy of orally administered BBT-401-1S in inducing a clinical response in subjects with active ulcerative colitis (UC) which is defined as have been diagnosed with active UC for ≥ 3 months prior to Day 1, have an inadequate response or disease relapse despite treatment of UC based on the local standard of care prior to screening, or have a total Mayo score ≥ 6 , and endoscopic subscore ≥ 2 , rectal bleeding subscore ≥ 1 , and a stool frequency subscore ≥ 1 , regardless of standard of care history.

The secondary objectives of the study are:

- to assess the safety and tolerability of orally administered BBT-401-1S
- to explore additional measurements of the efficacy of orally administered BBT-401-1S in inducing endoscopic and clinical remission.

The exploratory objectives of this study are to evaluate the effects of BBT-401-1S on endoscopic response, subject-reported outcomes, histological improvement, biomarkers, and long-term clinical remission.

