6.6.2 Secondary Efficacy Analysis

Centrally read Mayo endoscopic subscores will be used to evaluate the secondary objectives of the study.

The stool frequency and rectal bleeding subscores will use the average of the last 3 non-missing assessments recorded in the subject diary. If an endoscopy is performed, the average of the last 3 non-missing assessments recorded in the subject diary prior to bowel preparation should be used. If the subscore is not an integer, the subscore should be rounded to the nearest integer. Missing values will be considered as unresponsive as described in Section 5.2.

- **Clinical remission at Day 57, as measured by a total Mayo score of ≤ 2 points, with no individual subscore exceeding 1 point.**

Total Mayo Score will be calculated based on the response achieved from all 4 subscores ranged from 0-3 each out of a total sum of 12.

Subjects who have a sum of total Mayo score ≤ 2 points, with no individual subscore exceeding 1 point at Day 57, will be considered as achieving clinical remission.

The number and proportion of subjects with the 95% confidence interval (CI) of clinical remission rate at Day 57 will be calculated using the exact binomial method for each treatment. The Fisher's exact test will be used to evaluate any differences between treatments at Day 57 will be summarised for the induction phase by treatment group for then ITT Population.

- **Achievement of endoscopic remission at Day 57, as measured by a Mayo endoscopic subscore of 0 or 1.**

The number and proportion of subjects achieving endoscopic remission at Day 57 with the 95% CI will be calculated using the exact binomial method for each treatment. The Fisher's exact test will be used to evaluate any differences between treatments at Day 57 will be summarised for the induction phase by treatment group for the ITT Population.

- **Change from baseline to Day 57 in the Total Mayo score.**

Statistical Analysis Plan

Sponsor Name: Bridge Biotherapeutics, Inc.
Sponsor Protocol ID: BBT401-UC-005

Analysis of covariance (ANCOVA) with change from baseline as the dependent variable and baseline value as the covariate variable will be used to compare the change from baseline to Day 57 in the total Mayo score between each treated group and the placebo group. The 95% CI for the treatment differences in the change from baseline will be calculated, and the p-value will be provided.

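### SAP 6.6.5 describes UCEIS change but compares arms only on a 2-point yes/no cut with Fisher's exact test; at 12 v 12 that costs roughly half the effective sample for this exploratory endpoint

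*SAP*

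**What the plan says.** SAP 6.6.5 defines the first endoscopic response endpoint by a fall of at least 2 points, a "reduction from baseline in UCEIS score via central reading". On scoring: "The UCEIS score will be calculated as the sum of the scores of all descriptors". Protocol Appendix 5 gives the descriptor maxima as 2 (vascular pattern), 3 (bleeding) and 3 (erosions and ulcers), so the total runs from 0 to 8.

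The change is then turned into a count: "Baseline total UCEIS score minus Day 57 UCEIS score will be used to calculate the number of subjects" with the required fall. Each arm's rate gets an exact 95% CI, and "The Fisher's exact test will be used to evaluate any differences between treatments at Day 57". On the original scale the SAP says only "The actual and change from baseline will be presented". Protocol 8.4.2 likewise lists "Actual values and change from baseline in Mayo scores, UCEIS scores, IBDQ total score" among the items summarised descriptively. Neither document plans a model, a between-arm difference or a CI for a difference in UCEIS change.

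Other scores are treated differently. SAP 6.6.2 compares total Mayo using "Analysis of covariance (ANCOVA) with change from baseline as the dependent variable and baseline value as the covariate variable", with a 95% CI for each active arm against placebo. SAP 6.6.5 compares IBDQ and partial Mayo change, both exploratory, by MMRM.

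**The concern.** One exploratory objective (SAP 2.1) is to "evaluate the effects of BBT-401-1S on endoscopic response". UCEIS is read centrally and contains no subject-reported or physician-global item. After the cut, a 5-point fall counts the same as a 2-point fall, and a 1-point fall counts the same as a worsening.

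With about 12 subjects per arm, a yes/no comparison by a conservative exact test has little chance of showing an endoscopic effect that the same reads could show on their own scale. A flat Fisher result would say little, and the plan offers no adjusted difference with a CI to set beside it. Exploratory status does not explain the choice, because IBDQ and partial Mayo are exploratory too and are modelled on the full scale.

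**Working it through.** The documents state no UCEIS mean, SD, correlation, effect size, power or alpha, so there is no planned figure to reproduce.

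**Inputs from the documents.** 12 subjects per arm, 1:1:1 (SAP 2.2); scale 0 to 8 (2 + 3 + 3, Protocol Appendix 5); response = fall of at least 2 points.

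**Assumed.** Two-sided 5% (suggested by the 95% CIs); Fisher's test applied to one active arm against placebo; all means, SDs, correlations and effects below; no missing data.

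**1. What Fisher needs at 12 v 12.** For p ≤ 0.05 the smallest splits (active v placebo responders) are 5 v 0, 7 v 1, 8 v 2, 9 v 3 and 10 v 4. The true type I error is 0.3% to 2.3% at common response rates of 10% to 50%.

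**2. One case by hand.** SD of change σ = 2.0, placebo fall 0.5, extra fall δ = 2.0. An integer fall of at least 2 corresponds to a cut at 1.5.

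- Placebo rate: p0 = 1 − Φ((1.5 − 0.5)/2.0) = 0.309. Active rate: p1 = 1 − Φ((1.5 − 2.5)/2.0) = 0.691.
- Fisher power, summing Bin(12, p1) × Bin(12, p0) over all tables with p ≤ 0.05: 35.5%.
- Unadjusted comparison of means: noncentrality δ/(σ√(2/12)) = 2.449 on 22 df, power 64.9%.
- Fisher needs 23 per arm to match this, so its effective sample is 12/23 = 0.52.
- Cut alone, in large samples: [(p1 − p0)²/(p0q0 + p1q1)] ÷ [δ²/(2σ²)] = (0.1467/0.4267)/0.5 = 0.69.
- Remaining factor, from Fisher's conservatism at this n: 0.52/0.69 ≈ 0.75.

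**3. Over a grid.** With σ 1.5 to 2.5, placebo fall 0.5 to 1.0 and extra fall 1.5 to 2.5, Fisher needs 22 to 24 per arm to match a comparison of means at 12. That is an effective sample of 12/24 = 50% to 12/22 = 55%. The cut alone keeps 65% to 77% of the information.

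**4. Integer scores with ANCOVA.** Simulated baseline mean 5 (SD 1.2), placebo fall 0.5, scores rounded and held within the scale. Power, Fisher on the cut / ANCOVA of change on baseline:

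| Day 57 SD, correlation | Extra fall 1.0 | Extra fall 1.5 | Extra fall 2.0 |
|---|---|---|---|
| 1.5, 0.3 | 12 / 35% | 30 / 65% | 51 / 88% |
| 1.5, 0.5 | 15 / 40% | 38 / 71% | 66 / 93% |
| 2.0, 0.3 | 9 / 22% | 21 / 44% | 34 / 65% |
| 2.0, 0.5 | 11 / 26% | 25 / 49% | 46 / 74% |

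Under no effect, Fisher rejects in 1.4-2.0% of trials and ANCOVA in 4.7-5.5%. Repeat runs move cells by a point or two; they give about 19-38% v 43-71% at 1.5 points and 35-67% v 66-93% at 2.0.

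**5. Baseline adjustment.** It adds anything from almost nothing to about 8 points of power. The larger figure is at SD 1.5, correlation 0.3, extra fall 1.5: unadjusted t-test 58%, ANCOVA 66%.

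**6. Precision of the added estimate.** The 95% CI half-width is about t(21) × SD × √(1 − ρ²) × √(2/12). This gives 2.08 × 1.5 × 0.866 × 0.408 = 1.1 points to 2.08 × 2.0 × 0.954 × 0.408 = 1.6 points.

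**The case against.** **The SAP analyses the endpoint that the protocol defines.** The endpoint is a response rate, and an exact CI with Fisher's test suits a binary outcome. This stands. It is why the rate should remain as defined, with the full-scale analysis added beside it.

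**The data are not discarded.** Means and SDs of change will be tabulated by arm, so a reader could work out an unadjusted difference and CI. True, but the plan commits nobody to reporting one, and it would lack baseline adjustment.

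**Power is a weak yardstick.** The sample size has no formal basis, and Protocol 8.4.2 rules out formal hypothesis tests on exploratory endpoints. This is fair. The power figures serve here as a measure of lost precision. The protocol statement also sits awkwardly with the SAP's own Fisher test, whereas an estimate with a CI is compatible with it. Even ANCOVA has only 22-40% power at an extra fall of 1 point.

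**The size rests on assumptions**, including a uniform shift. If the same mean effect (1.5 points) falls on half the subjects, power is 17-28% for Fisher and 35-52% for ANCOVA. The gain shrinks to 18-24 points but remains.

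**Two stronger readings are tempting but unsupported.** A reader might infer that most of the UCEIS information is lost. The cut alone loses about a quarter to a third, and the total is about half. A reader might also infer that UCEIS gets the weakest comparison of the disease measures. It does not: in SAP 6.6.5 the Mayo endoscopic subscore and modified Mayo are also compared only as yes/no outcomes, histology gets a shift table without a test, and the biomarkers are descriptive only.

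**Conclusion.** The point holds as a cheap improvement. UCEIS change is described but not compared, and the sole between-arm comparison is worth roughly half the sample that a full-scale analysis would use. Three sources contribute: the 2-point cut, Fisher's conservatism at 12 per arm, and the lack of baseline adjustment, which matters least and in some cases hardly at all.

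The direction was the same in every scenario with a treatment effect. The size depends on assumed SDs, correlations and effects and on complete data. The consequence is limited to signal-finding on an exploratory endpoint. The documents do not support the inference that the 2-point response rate is wrong or should be replaced, or that the primary or secondary conclusions are affected.

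**What to change.** Keep the 2-point response rate with its exact CI, and add to SAP 6.6.5:

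> Change from baseline (screening) to Day 57 in centrally read UCEIS total score will be analysed by ANCOVA with baseline UCEIS as covariate, using the 6.6.2 model. Adjusted mean differences of each BBT-401-1S group from placebo, and of BID from QD, will be given with 95% CIs, as exploratory estimates without a formal hypothesis test (protocol 8.4.2).

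ANCOVA suffices because UCEIS has only one scheduled post-baseline read in induction, unlike IBDQ and partial Mayo, which are also collected on Day 29.

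State how missing Day 57 reads and rescue are handled in this model. The schedule has UCEIS only at screening and Day 57 in induction, so the carry-forward rule in SAP 5.2 will seldom have a value to use. Its fallback of counting the subject as a non-responder has no equivalent for a mean change. The SAP 5.2 rescue rule is written for the primary and secondary responder analyses. One option is observed cases, plus a sensitivity analysis that sets missing or rescued subjects to no change.

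List the addition in SAP section 7.

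**Cost.** SAP wording and one more exploratory table, with a sensitivity version; no new data, visits, reads or subjects. The downside is one more result to interpret, in points rather than as a rate.

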6.7 Safety

6.7.1 Extent of Exposure

Duration of exposure will be defined in days as:

Overall Exposure:

(date of the last dose – date of the first dose) + 1-off-drug days

If date of the first dose date is missing, then the date of the first dose dispensed will be used. If the last dose date is missing then, then the last available dose date will be used.

Induction Phase Exposure:

(date of the last dose from the induction phase – date of the first dose from the induction phase) + 1-off-drug days

If date of the first dose date is missing, then the date of the first dose dispensed in the induction phase will be used. If the last dose date is missing then, then the last available dose date in the induction phase will be used.

Statistical Analysis Plan

Sponsor Name: Bridge Biotherapeutics, Inc.
Sponsor Protocol ID: BBT401-UC-005

Extension Phase Exposure:

(date of the last dose from the extension phase – date of the first dose from the extension phase) + 1-off-drug days

If date of the first dose date is missing, then the date of the first dose dispensed in the extension phase will be used. If the last dose date is missing then, then the last available dose date in the extension phase will be used.

Duration of exposure will be listed and summarised using descriptive statistics for each phase and overall by treatment group for the Safety Population.

The number and percentage of subjects with an overall duration of exposure in the following categories will be summarised for each phase and by treatment group for the Safety Population:

- <22 days
- ≥ 22 and <57 days
- ≥ 57 days

Overall duration will be summarised by treatment received during the induction phase. Exposure during each study phase will be summarised by the actual treatment received respectively during each study phase.

